1.2 Inclusion Criteria by Staging

Stage 0 (DCIS), Stage I-II patients (T1-2N0 M0) with breast cancer patients who undergo adjuvant whole breast radiotherapy.

2 Background and Hypotheses

Breast conserving surgery and adjuvant whole breast radiotherapy is a standard treatment option for most patients with early-stage invasive breast cancer [1]. Hypofractionated whole breast irradiation (HF-WBI) has become a standard radiotherapy fractionation regimen and is usually delivered over 15 to 16 fractions [2]. With greater than 10 years of follow up, several large randomized clinical trials have shown similar local control and overall survival [3-7]. Recent randomized evidence indicates that patient convenience, quality of life, and breast cosmetic outcome may be better with the shorter treatment course [5,8]. Given the advantages and increasing nationwide utilization of the shorter radiation treatment course, we are conducting a randomized, phase III non-inferiority clinical trial to test the hypothesis that hypofractionation over two weeks is not inferior to treatment over three weeks when delivering whole breast radiotherapy with a concomitant boost.

2.1 Advantages of hypo-fractionation

The advantages of shorter treatment courses in whole breast radiotherapy have led to better understanding of the properties of tumor control and normal tissue tolerances. Several large

randomized clinical trials have now led to wide acceptance that whole breast radiotherapy over 15 to 16 fractions leads to similar tumor control outcomes. The START trials and a randomized trial from MDACC would suggest that patients may also have better quality of life and cosmetic outcomes with shorter fractionation courses.

Delivering a tumor bed boost concurrently can further shorten a patient's radiation treatment course to three weeks. A series of PHASE II prospective clinical trials have established the safety and efficacy of delivering the boost concomitantly [9-11]. A large RTOG study, RTOG 1005, has completed accrual and should report randomized results shortly [12]. The IMPORT High trial in the United Kingdom has reported similar cosmetic outcomes for the effect on breast appearance between a concurrent boost regimen with a sequential boost regimen. With the trend towards shorter treatment courses in the adjuvant breast radiotherapy setting, we are proposing a study to investigate the equivalence of delivering whole breast irradiation in two weeks with a equivalent radiobiologic effective dose.

2.2 The NYU experience of three weeks whole breast radiotherapy with a concomitant boost

Our group has developed extensive experience with hypofractionated whole breast irradiation over three weeks, most notably over a series of four prospective clinical trials. From 2003 to 2015, we conducted five investigator-initiated trials that resulted in local control and cosmetic outcomes comparable to those achieved by the original six-week regimen of whole breast radiotherapy and sequential boost to the tumor cavity. The series of prospective trials showed that the shorter regimen was associated with decreased acute toxicity [13], that prone technique and IMRT allowed for decreased radiation doses to the heart and lung tissues [14,15] while assuring efficacy [16], and that regional nodal treatment in prone position was also safe and well tolerated over three weeks [17]. More recent analysis demonstrated avoidance of radiation to the left anterior descending artery when our prone breast technique is adopted [18], and that excellent outcomes and cosmesis are also achieved in women younger than 50 years old [19]. Based on the safety, efficacy and greater convenience demonstrated with the shorter hypofractionation schedules, we now propose to investigate a two-week whole breast irradiation course, in the attempt to establish a new standard of care.

2.3 Optimal accelerated fractionated regimen of 10 fractions delivered over 2 - weeks.

The optimal accelerated dose fractionation for external beam whole breast irradiation remains to be established. One of the main objectives of this study will be to determine the acute and late effects using a regimen of 10 fractions. Our current standard of care treatment is the fifteen fractions regimen. Only minimal acute effects resulted from this regimen [16].

The biologically equivalent doses of different fractionation schedules are the total doses for which the probabilities of a certain outcome/complication are the same. They can be different for specific outcomes/complications. The biologically equivalent doses in regard of several outcomes/complication to a treatment delivered in the standard 2 Gy fractions five times a week was estimated by the widely used formula [20-23]:

$$D_{new} = D_{ref} * (\alpha / \beta + d_{ref}) / (\alpha / \beta + d_{new})$$

or - in this case - using 5 fractions of dref dose:

$$D_{\text{new}} = 5 * d_{\text{ref}} * (\alpha / \beta + d_{\text{ref}}) / (\alpha / \beta + 2)$$

where α / β is a tissue dependent parameter, arising from the radiobiological linear - quadratic cell survival model.

From the randomized prospective trials, there is an estimate that breast cancer may have an alpha/beta for tumor control of 4.6 and normal breast tissue an alpha beta ratio of 3.4 [6]. The relative closeness in alpha/beta ratios of tumor and normal tissue would support a rationale for hypo-fractionation [20-23]. Based on the formula above, Table 1 includes the calculation of BEDs (biologically equivalent doses) between the 2 arms. The breast cavity is predicted to have an alfa/beta value between 3-4.

Based on Table 1 a regimen of 42 Gy in 10 fraction to the boost is comparable to 48 Gy in 15 fractions. The latter regimen has been proven to both be effective (local recurrence rate <5% at 5 years) and to be associated with excellent cosmetic results (16), justifying our choice for a biologically equivalent regimen) in the experimental arm comparable to standard arm (see α/β values in Table 1, in bold).

In view of the fact that most recurrences tend to occur at the original tumor bed and that other studies have shown efficacy of lower doses of adjuvant radiation to the rest of the breast (4-8), we elect to test a dose of 32 Gy in 10 fractions. Maintaining a relative low dose to the rest of the breast tissue, which is a much lower risk of local recurrence than the area of the tumor cavity, will reflect on very low risk of fibrosis and will enhance the likelihood of optimal breast symmetry and cosmesis.

TABLE 1

Alfa/Beta (Gy)	2 Gy x 23	2.7 Gy x 15	3.2 Gy x 15*	3.2 Gy x 10	4.2 Gy x 10*
2	46	47	62.4	41.6	65.1
3	46	46.1	59.5	39.68	60.48
4	46	45.2	57.6	38.4	57.34
10	46	42.8	52.8	35.2	49.7

- Boost Dose delivered at tumor bed

3 Staging Criteria

TNM Stage 0 (Tis N0 M0), Stage I-II, T1-2 N0 M0, newly diagnosed breast cancer patients.

4 Patient Eligibility

Inclusion criteria:

1. Women status post segmental mastectomy
2. If unilateral, pT1-2 breast cancer excised with negative margins
3. If bilateral, pT1-2 breast cancer excised with negative margins AND/OR pTis excised with negative margins.
4. Clinically N0 or pN0 or sentinel node negative
5. Ductal carcinoma in situ DCIS with negative margins (no DCIS on inked margins).
6. Women with previous contralateral breast cancer.

Exclusion criteria:

1. Previous radiation therapy to the ipsilateral breast.
2. 90 days from last surgery, unless s/p adjuvant chemotherapy
3. 60 days from last chemotherapy
4. Male breast cancer

5 Descriptive Factors/Stratification/Randomization Scheme

This is a prospective, randomized study. No stratification is planned. The study schema describes the study design.

5.1 Study Schema /Table 2

Eligibility	Stage 0 or Stage I-II breast cancer s/p segmental mastectomy.	
Day 0	Informed consent and randomization CT planning for determination of tumor bed on the prone position	
Days 1-15 (start within 90 days from last breast surgery)	Weekly IGRT, IMRT or Conformal breast irradiation, randomly assigned to: 15 fractions whole breast radiotherapy with concomitant boost (arm 1) or 10 fractions whole breast radiotherapy with concomitant boost (arm 2)	
Note: Patients with bilateral breast cancer will be randomized to receive the same dose and fractionation to both breasts		

6 Treatment plan

6.1.1 The women in this study will be randomly assigned to receive either 10 or 15 radiation fractions. The study design permits to test non inferiority of the 2 weeks versus 3 weeks regimen in terms of acute toxicity, fibrosis, breast cosmetic results and local control at 2-3 years and at 5 years follow up.

6.1.2 The informed consent process is as follows. The principal investigator explains all elements of the protocol to the patients and answers any and all questions. Clinical procedures are performed by the principal investigator. The research nurse will obtain blood sample by venipuncture. The consent process takes place in the Department of Radiation Oncology at Weill Cornell Medical Center. The consent form process is concluded when the patient, principal investigator and the witness all have signed the consent form. The witness is a present adult able to verify that the patient was given the proper information needed to make an informed decision to participate in the clinical study. year 1

6.1.3 Once the process of randomization is concluded, patients will be informed of the schedule based on the assigned one of the 2 arms.

6.1.4 Simulation and treatment will be started within 90 days from surgery, in order to maximize the chances of optimal lumpectomy cavity visualization on the planning and cone beam CT scans.

6.1.5 Our routine follow up is once a year after completion of radiation therapy. For the purpose of protocol significance (for assessment of fibrosis), we will require at least one follow up visit to our department, after years 2. (See 11.1 Study calendar).

Breast cosmesis will be self-assessed by the patient using BCTOS questionnaires, before treatment (baseline), at the end of RT, at 1-month follow up visit and at 2-year follow up visit. The receipt of the survey will be recorded by the research nurses assigned to the study, but completion is not mandatory. Quality of life surveys will be sent to the patients' personal email address at the baseline, at the end of RT, at 1-month follow up visit and at 2-year follow up visit. Completed responses will be sent directly to our REDCAP database. The quality of life survey completion is optional.

7 Radiation Therapy

7.1 Immobilization Techniques:

Patients will be set-up for CT simulation and treatment utilizing a dedicated table designed to accommodate prone positioning for breast treatment [22].

7.2 CT simulation

A treatment planning CT of the breast will be acquired with the patient in the treatment position (prone), utilizing the same immobilization devices as will be used for treatment. CT scan thickness should be < 0.375 cm through the tumor bed region. These images will be used in treatment planning of the breast in accordance with the dose specification constraints. Contouring of tumor bed, indexed and contralateral breast tissue, thyroid, ipsilateral and contralateral lung, heart and left anterior descending artery (LAD) will be performed in order to guide beam arrangement and optimal normal tissue avoidance. The patient will be CT scanned in the supine position if the patient cannot lie prone, or if the prone plan is not acceptable. Specifically supine set up will be attempted if the dosimetry information derived from prone planning reveals exceeding normal tissue dose constraints for heart,

LAD, ipsilateral lung, or contralateral lung.

7.3 Treatment duration

The whole breast will be treated for five consecutive fractions for either three (Arm 1) or two (Arm 2) consecutive weeks.

7.4 Target Delineation

- 7.4.1 The PTVBreast is the entire breast volume acquired in prone or supine position based on physician's delineated fields. The PTVBreast is derived from the 50% isodose line associated with clinically determined opposed tangent fields. This is accomplished by converting the 50% isodose level to a structure, smoothing and then removing parts extending outside the 50% isodose structure with an additional 0.7 cm margin within the field borders. The lung and the heart are also excluded from the PTVBreast volume.
- 7.4.2 The GTV is the tumor bed, as identified on CT.
- 7.4.3 The PTVTumor is the GTV with an additional 1.0 cm 3D margin. PTVTumor will not extend outside of the breast tissue and, if necessary, will be consistently modified ("clipped") to be confined within PTVBreast.

7.5 Normal structure delineation

The following structures will be contoured: contralateral breast, thyroid, ipsilateral lung, contralateral lung, heart, and LAD

7.6 Technical Factors

- 7.6.1 Dose calculation with heterogeneity corrections must be used.
- 7.6.2 Nominal photon energies greater than or equal to 6 MV must be used. 16 MV photons may be used mixed with 6 MV photons in a ratio not to exceed 3:1 (16 MV: 6 MV). However, 16 MV photons may not be used for any beam in which the superficial extent of the GTV is within 0.5 cm of the skin.
- 7.6.3 Prone positioning requires the isocenter to be placed approx. 1.5 cm from medial edge of the breast to allow clearance between the gantry and the couch/board.
- 7.6.4 Hybrid Whole Breast planning - IMRT (intensity modulated radiation therapy) tangents plus non-IMRT tangents
 - 1. Non-IMRT tangents deliver nominally 67% of prescribed dose using 6 MV or 6MV/16MV photons and include 3 cm anterior flash. The fields are wedged and weighted to obtain a uniform dose distribution, normalized to allow approximately 105% dose max.
 - 2. IMRT tangents deliver nominally 33% of prescribed dose using 6 MV photons and include 3 cm anterior flash and use the non-IMRT tangent plan as a base for optimization. 3D-CRT Whole Breast Planning
 - 3. 3D-CRT tangents will be used to obtain a uniform dose distribution.

4. Wedges and/or field within fields can be used.

7.6.5 Boost plan

1. Non-coplanar beam arrangement is encouraged, but not required
2. Electrons, 3D-CRT or IMRT may be used
3. If the tumor bed, as visualized in the BEV (beams-eye-view), is within 1cm of the body surface, 1 cm of flash will be added to the field(s)
4. No photon beam will be directed toward heart, lung, contralateral breast, or thyroid
5. Inclusion of soft tissue not irradiated by the whole breast tangents is allowed to aid in target coverage

7.6.6 Dose Constraints

Target volume dose constraints for Whole Breast Plans: Whole breast IMRT hybrid tangents. PTVBreast max 108% (to $\geq 1\text{cc}$) of the whole breast dose. This can be achieved with 6 MV, or 6 MV/16 MV (IMRT/3D) photons. PTVBreast: $\geq 95\%$ of the volume must receive $\geq 100\%$ of the whole breast dose. PTVTumor: $\geq 98\%$ of the volume must receive $\geq 100\%$ of the whole breast dose.

Whole breast 3D-CRT tangents PTVBreast max 112% (to $> 1\text{cc}$) of the whole breast dose. PTVBreast: $\geq 95\%$ of the volume must receive $\geq 100\%$ of the whole breast dose. PTVTumor: $> 98\%$ of the volume must receive $> 100\%$ of the whole breast dose.

Target volume dose constraints for Boost Plans:

IMRT Boost

Breast max 108% (to $> 1\text{cc}$) of the boost dose. This can be achieved with 6 MV IMRT, or a hybrid approach using 6 MV/16MV (IMRT/3D) photons.

PTVTumor: $> 98\%$ of the volume must receive $> 100\%$ of the total boost dose.

$> 60\%$ of the PTVBreast volume must not receive $> 50\%$ of the total boost dose.

3D-CRT Boost

Breast max 112% (to $> 1\text{cc}$) of the boost dose. This can be achieved with 6 MV, 16 MV, or 6MV/16 MV photons.

PTVTumor: $\geq 98\%$ of the volume must receive $\geq 100\%$ of the total boost dose.

$> 60\%$ of the PTVBreast volume must not receive $> 50\%$ of the total boost dose

Composite of tangents and boost fields.

TABLE 3

Target/Normal Tissue Dose specifications	
Target Volume/Normal Tissue	Dose Constraints
PTVTumor	V48 Gy $\geq 98\%$
PTVBreast/Chest Wall	V40.5 Gy $\geq 95\%$
PTVNodes	V38.5 Gy $\geq 95\%$
Heart	V5 Gy $< 5\%$
Ipsilateral Lung	V10 Gy $< 20\%$
Spinal Cord	37.5 Gy maximum*
Esophagus	36 Gy maximum*
Brachial Plexus	42 Gy maximum*

PTVTumor: $> 98\%$ of the volume must receive $> 100\%$ of the total dose, where total dose is the whole breast dose plus boost dose.

PTVBreast: $> 95\%$ of the volume must receive $> 100\%$ of the whole breast dose.

PTVBreast: no more than 60% of PTVBreast should receive $> 4455\text{ cGy}$

Normal tissue dose constraints:

Heart: $< 5\%$ of the heart receives $> 5\text{ Gy}$.

Ipsilateral lung: $< 15\%$ of the ipsilateral lung receives $> 10\text{ Gy}$.

Contralateral lung: $< 15\%$ of the contralateral lung receives $> 5\text{ Gy}$. LAD: maximum $< 1800\text{ cGy}$, mean $< 1000\text{ cGy}$.

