Intervention Description: Radiotherapy: 4050cGy whole breast radiotherapy with a concomitant tumor bed boost to 4800 cGy to the tumor bed in 15 fractions (Arm 1) versus 3200cGy whole breast radiotherapy with a concomitant tumor bed boost to 4200 cGy in 10 fraction (Arm 2).

Hypothesis: A regimen of whole breast radiotherapy to 3200cGy with a concomitant tumor bed boost to 4200 cGy in 10 fractions (Arm 2) is not inferior to the current standard of whole breast radiotherapy of 4050 cGy with a concomitant tumor bed boost to 4800 cGy in 15 fractions (Arm 1), in terms of acute toxicity and long-term fibrosis, breast cosmesis and local control, at 2-3 years and at 5 years.

Primary Objectives: 1. To prospectively randomize patients to one of two hypo-fractionation regimens of concomitant boost breast radiotherapy as part of breast conservation therapy in patients with T1-2N0 breast cancers or Stage 0 (Tis) DCIS: 4050cGy whole breast radiotherapy with a concomitant tumor bed boost to 4800 cGy to the tumor bed in 15 fractions (Arm 1) versus 3200 cGy whole breast radiotherapy with a concomitant tumor bed boost to 4200 cGy in 10 fractions (Arm 2).

2. To test the primary hypothesis that the proportion of patients with grade ≥ 2 acute toxicity with 2 weeks regimen (10 fraction arm) would not be $> 5\%$ greater than the rate of 10% with a standard 3weeks regimen (15 fraction arm).

Endpoints:

Primary endpoint is the rate of acute toxicity. Expected acute toxicities include fatigue and skin reactions within the radiation field. Erythema, dry and wet desquamation of the skin will be recorded weekly, during RT treatment. The toxicities will be graded by the research nurses assigned to the study according to Common Terminology Criteria for Adverse Events, version 5.0.

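### Table 3 in section 7.6.6 sets target coverage at Arm 1 doses with no arm label, so no Arm 2 plan at its prescription can comply; one breast-volume cap and one lung limit also need correcting.

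*Combined protocol and SAP*

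**What the plan says.** The Protocol Summary (Intervention Description) gives the two regimens: "4050cGy whole breast radiotherapy with a concomitant tumor bed boost to 4800 cGy to the tumor bed in 15 fractions (Arm 1") and "3200cGy whole breast radiotherapy with a concomitant tumor bed boost to 4200 cGy in 10 fraction (Arm 2").

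Section 7.6.6 then sets plan-acceptance rules in two forms.

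- **Table 3** uses absolute doses and names no arm: PTVTumor V48 Gy at least 98%, PTVBreast V40.5 Gy at least 95%, ipsilateral-lung V10 Gy below 20%.
- **The text before and after the table** mostly uses percentages. Coverage is set at 100% of the whole-breast dose for PTVBreast and of the total dose for PTVTumor, "where total dose is the whole breast dose plus boost dose". Maxima are 108% for IMRT and 112% for 3D-CRT, for whole-breast and boost plans alike. A further boost-plan rule limits how much of PTVBreast may receive over half of the total boost dose.

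The text under the table also has one absolute target limit, "PTVBreast: no more than 60% of PTVBreast should receive" more than 4455 cGy, and its own lung limit: less than 15% "of the ipsilateral lung receives" more than 10 Gy.

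The Arm 2 doses of 42 and 32 Gy do not appear anywhere in section 7.6.6.

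**The concern.** Table 3 decides whether a plan is acceptable. If its target rows hold only for Arm 1, the experimental arm has a written rule that conflicts with its randomised prescription. A planner must then choose between the table and the percentages, and a departure in Arm 2 cannot be classified consistently. Sites beyond the lead center also enroll, so the rule should not depend on local understanding.

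At stake are fibrosis and cosmesis, both secondary endpoints. Section 2.3 justifies the low 32 Gy breast dose by its expected benefit for exactly these outcomes, so a plan pushed toward the Table 3 doses would undo that choice.

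The 4455 cGy cap and the lung limit are separate matters. The first is loose in Arm 2. The second is an inconsistency that affects both arms equally.

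**Working it through.** **Inputs.** Arm 1: 40.5 Gy whole breast, 48 Gy tumor bed, 15 fractions. Arm 2: 32 Gy, 42 Gy, 10 fractions (Protocol Summary). The limits are those of section 7.6.6.

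**1. Origin of the absolute figures.** 48 and 40.5 Gy are 100% of the Arm 1 doses. 1.10 × 4050 = 4455 cGy exactly. The 1.10 factor is inferred; the protocol does not state it.

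**2. Table 3 target rows against Arm 2 (Gy).**

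| Target | Table 3 | Arm 2 dose | Ratio | 108% | 112% |
|---|---|---|---|---|---|
| PTVTumor | 48 | 42 | 1.143 | 45.36 | 47.04 |
| PTVBreast | 40.5 | 32 | 1.266 | 34.56 | 35.84 |

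Both Table 3 doses lie above both maxima.

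The tumor-bed maxima above take 42 Gy as the base. If the boost dose is instead the increment, 42 − 32 = 10 Gy, the ceilings add up:

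- IMRT for both plans: 34.56 + 10.8 = 45.36
- 3D-CRT for both plans: 35.84 + 11.2 = 47.04
- Mixed: 34.56 + 11.2 = 45.76, or 35.84 + 10.8 = 46.64

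All are below 48. Section 7.6.5 also allows an electron boost, for which 7.6.6 gives no maximum; there the conflict is with the prescription alone.

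The PTVBreast maxima apply to the whole-breast plan, while Table 3 is headed as a composite. Boost spill would have to add 40.5 − 32 = 8.5 Gy, or 85% of a 10 Gy boost, to 95% of the breast. With the boost taken as 10 Gy, the boost-plan volume rule holds spill to 5 Gy in at least 40% of the breast, however its 60% is parsed. At prescription that part receives about 32 + 5 = 37 Gy, short of 40.5. The PTVTumor row alone already makes the table unattainable at the Arm 2 prescription.

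**3. What the excess would mean biologically.** Section 2.3's formula for n fractions of d Gy gives the 2-Gy equivalent n × d × (α/β + d)/(α/β + 2). With α/β = 3:

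- 4.2 Gy × 10: 42 × 7.2/5 = 60.48 (matches Table 1)
- 3.2 Gy × 10: 32 × 6.2/5 = 39.68 (matches Table 1)
- 48 Gy in 10: 48 × 7.8/5 = 74.9
- 40.5 Gy in 10: 40.5 × 7.05/5 = 57.1

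These last two are hypothetical: they show what literal use of Table 3 in Arm 2 would deliver.

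**4. The 4455 cGy cap.** 44.55/48 = 0.93 of the tumor-bed dose in Arm 1, but 44.55/42 = 1.06 in Arm 2. Against the whole-breast dose it is 1.10 in Arm 1 and 44.55/32 = 1.39 in Arm 2. In Arm 2 only hot spots between 44.55 Gy and the 45.36 or 47.04 Gy maximum could exceed it, so a limit on 60% of the breast is met by almost any plan. The same 1.10 factor would give 1.10 × 3200 = 3520 cGy.

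**5. Ipsilateral lung.** The limits differ by 20 − 15 = 5 percentage points. A plan at 17% passes Table 3 and fails the text. Section 7.2 calls for a supine attempt when prone planning exceeds the lung constraint, so for plans between 15% and 20% that trigger is ambiguous.

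**The case against.** The strongest reply is that this is a drafting slip with little practical reach. Table 3 also lists nodes, spinal cord, esophagus and brachial plexus in an N0 trial whose section 7.4 defines no nodal target, so it looks carried over from elsewhere. The Arm 2 prescription is stated consistently, the percentage rules work in Arm 2, and a planner would have to override the prescription by 14% to 27% to follow the table. That conflict would be obvious at planning.

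Most of this stands, and it rules out several stronger readings that a reader might infer:

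- *That Arm 2 patients were overdosed.* Nothing in the documents shows that Table 3 was applied in Arm 2.
- *That section 7.6.6 gives no usable Arm 2 targets.* The percentage-based text does.
- *That the 4455 cGy line blocks Arm 2 plans, or leaves Arm 2 with no limit on spill.* It is slack in Arm 2, and the relative boost-plan limit and the whole-breast maxima still apply.
- *That the lung mismatch makes Arm 2 infeasible or favors an arm.* Staying below 15% meets both limits, and neither depends on arm.
- *That the arm comparison is confounded.* The arms differ by design in total dose, fraction size and breast-to-boost ratio. No effect on the primary endpoint, acute toxicity of grade 2 or higher, can be derived from the documents.

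The reply does not remove the defect. The table is unlabelled, stands as a requirement, and is wrong for the experimental arm.

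**Conclusion.** The point holds in limited form. Two target rows of Table 3 are Arm 1 values presented as general. They sit 14% and 27% above the Arm 2 prescription and above the section's own maxima, so an Arm 2 plan at its prescription cannot meet the table, while the percentage-based text remains workable. The 4455 cGy line is about 6% above the Arm 2 tumor-bed dose and restrains almost nothing there. The two lung limits differ by 5 percentage points in both arms.

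The risk to safety and to comparability of the arms is potential and has not been shown. The verdict assumes that Table 3 is meant for both arms, since it carries no label. The tumor-bed result is the same whether the boost maximum is taken on the total dose or built up from the increment. The 110% factor is inferred and matters only for the suggested Arm 2 cap.

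**What to change.** 1. Label the present PTVTumor and PTVBreast rows of Table 3 as Arm 1 and add Arm 2 values: V42 Gy at least 98% and V32 Gy at least 95%. Alternatively, express both rows as a percentage of the arm's prescription.
2. State the 60% breast-volume cap per arm. On 110% of the whole-breast dose it is 4455 cGy in Arm 1 and 3520 cGy in Arm 2. Physics should confirm this. The room above the whole-breast dose is 4.05 Gy of a 7.5 Gy boost (54%) in Arm 1 but 3.2 Gy of a 10 Gy boost (32%) in Arm 2, so the same percentage is stricter in Arm 2.
3. State one ipsilateral-lung V10 limit. Below 15% satisfies both current limits; the choice belongs to the radiation oncology and physics team.
4. Check and record which constraints were applied to Arm 2 patients already planned. Section 11 defines no per-protocol or sensitivity analysis, so any analysis that uses this record would have to be specified first.

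The cost is a short amendment to one table and one paragraph, plus the plan check. Sample size and the primary analysis are unaffected.
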